3.2 Description

LB-102 (Figure 1) was created by adding a methyl group to the aniline nitrogen of amisulpride.

Figure 1: Structure of LB-102

Molecular Weight: 383.51

3.3 Nonclinical Pharmacology

3.3.1 Pharmacodynamics

In rodents, amisulpride preferentially blocks post-synaptic D₂ receptors in the limbic structures (responsible for affective and cognitive processes) preferentially over those in the striatum (responsible for extrapyramidal effects). In addition, amisulpride does not induce catalepsy and it does not produce D₂ hypersensitivity after repeated treatment. Amisulpride preferentially blocks pre-synaptic D₂/D₃ dopamine receptors at low doses, producing the dopamine release that is responsible for its disinhibitory effects. In animal preclinical models of schizophrenia amisulpride has been demonstrated to mimic current antipsychotics in the amphetamine induced hyperactivity (Perrault et al., 1997) and conditioned avoidance response (Natesan et al., 2008) models.

The pharmacodynamics of amisulpride are well-established (Solian Label, 2017), and based on the physicochemical attributes of LB-102 measured to date suggest they will be similar.

3.4 Clinical Experience and Pharmacokinetics

LB Pharmaceuticals has not conducted any studies of LB-102 in humans, however pharmacokinetic data from prior studies in mice, rats, and dogs have provided initial feedback on how the pharmacokinetic (PK) profile LB-102 compares to amisulpride.

A study was conducted to compare the PK of LB-102 to amisulpride in rats following a single oral dose at 3 mg/kg. The total plasma concentrations of benzamide, which includes LB-102 and its metabolite amisulpride, were found to be equivalent in LB-102- and amisulpride-treated rats (Figure 2).

[figure not shown]

Figure 2: Plasma Concentration Vs. Time Curves Following Single Oral Dose at 3 mg/kg of LB-102 (Exposures To Amisulpride Plus LB-102) or Amisulpride (Exposures to Amisulpride) in Rats

A mouse PK study of LB-102 in mice was also conducted following a single oral dose of 30 mg/kg amisulpride or LB-102, and data for the total benzamide concentrations are depicted in Figure 3. In concordance with the rat PK data, about 50% of LB-102 is metabolized into amisulpride and the total plasma concentration of benzamide after oral dosing LB-102 was consistent with that of amisulpride.

[figure not shown]

Figure 3: Pharmacokinetic Profile of 30 mg/kg Dose PO to Mice (n = 3/group)

Preliminary pharmacokinetic studies show that LB-102 behaves similarly to amisulpride in both mice and rats.

4. OBJECTIVES

The Primary Objectives:

Part A (SAD)

• To evaluate the safety and the tolerability of a single oral dose of LB-102 compared to placebo

Part B (MAD)

 To evaluate the safety and the tolerability of multiple oral doses of LB-102 compared to placebo

The Secondary Objectives:

Part A (SAD)

• To evaluate the PK of a single dose of LB-102

Part B (MAD)

• To evaluate the PK of multiple oral doses of LB-102

5. STUDY DESIGN

5.1 Overall Study Design and Plan

This is a Phase 1, randomized, double-blind, placebo-controlled study designed to evaluate the safety, tolerability, and PK of LB-102 in healthy subjects. The study will consist of two parts: Part A – Single Ascending Dose and Part B – Multiple Ascending Dose. There will be 5 cohorts in Part A and 3 Cohorts in Part B of this study. The following schedule represents the ideal study schedule. It should be used as guidance for study conduct. In the event there are delays at any visit days that may affect the dates of any subsequent visit, the planned days may vary.

In Part A, eligible subjects, in 5 cohorts, will be randomized on Day 1 (pre-dose) to placebo (n=2) or LB-102 (n=6) treatment for a total of 40 subjects. Four (4) visits will occur as follows: Screening (Visit 1, Days -28 to -1), Check-in (Visit 2, Day 0), Treatment Evaluation (Visit 3, Days 1-3), and Follow-up (Visit 4, Day 8 and Visit 5, Day 15 [for Cohort 5, Part A only]). The study procedures for these visits are presented in detail in Table 1. Dosage of LB-102 will begin at 50 mg/day and subsequent groups will administered 10, 100, 200, and 150 mg/day, respectively. In Cohort 1 (Part A), dosing of the first 2 subjects (1 active and 1 placebo) will commence at least 24 hours prior to the remaining 6 subjects. Dosing of the remaining subjects in the cohort may proceed if no safety issues are identified for the first 2 subjects. On Day 1, following a 12-hour overnight fast, subjects will receive 1 oral dose of placebo or LB-102 at 8 AM (±1 hour). For each cohort, blood samples for PK will be collected on Day 1 at pre-dose and at 15, 30, and 45 minutes (±5 min), and 1, 1.5, 2, 3, 4, 6, 8, 12, 16, 24, 32, and 48 hours (±15 min) post-dose, and Day 8 and Day 15. Vital signs will be recorded for each subject at Screening, Check-in, Day 1 at pre-dose and at 0.5, 1, 1.5, 2, 4, 6, 8, 12, 24, and 48 hours (±30 min) post-dose, and at the Follow-up visit (Day 8). 12-lead ECG will be done on at Screening, Check-in, Day 1 at pre-dose and 1, 2, 3, 4, 5, 6, 8 and 24 hours (±30 min) post-dose. ECG will be measured once at each time point for Cohorts 1-4 and in triplicate for Cohort 5. Clinical labs (hematology, chemistry, urinalysis) will be assessed at Screening, Check-in, Day 2, and Follow-Up. Hemoglobin A1c (HbA1c) will be measured in serum at Screening, Prolactin will be measured in serum at Screening, Day 3, Day 8, and Day 15, C-SSRS will be assessed at Screening and Day 3. Subjects will remain in the clinic from Check-in to Discharge on Day 3 for additional safety assessment and then return for a Follow-up Visit on Day 8. Subsequent groups will follow the same study procedures.

In Part B, eligible subjects, in 3 cohorts, will be randomized on Day 1 (pre-dose) to placebo (n=2) or LB-102 (n=6) treatment for a total of 24 subjects. Four (4) visits will be scheduled for this study: Screening (Visit 1, Days -28 to -1), Check-in (Visit 2, Day 0), Treatment Evaluation (Visit 3, Days 1-9), and Follow-up (Visit 4, Day 15). The study procedures for these visits are presented in

detail in Table 2. Dosage of LB-102 will be based on the PK observed in a minimum of two Part A cohorts. Subjects will receive 2 doses of placebo or LB-102, first dose at 8:00 AM (±1 hour) and second dose approximately 12 hours later, on Days 1-6 and one dose at 8 AM (±1 hour) on Day 7 for a total of 13 oral doses. The first dose on Day 1 will occur following a 12 hour, overnight fast. For each cohort, blood samples for PK will be collected at multiple timepoints starting on Day 1 at pre-dose and at 15, 30, and 45 minutes (±5 min), and 1, 1.5, 2, 3, 4, 6, 8, 12, and 16 hours (±15 min) post first dose. On Days 2-6, blood samples for PK will be collected prior to the first dose. On Day 7 blood samples for PK will be collected pre-dose and at 15, 30, and 45 minutes $(\pm 5 \text{ min})$, and 1, 1.5, 2, 3, 4, 6, 8, 12, 16, 24, 32, and 48 hours $(\pm 15 \text{ min})$ post first dose. Vital signs will be recorded for each subject at Screening, Check-in, Day 1 at pre-dose and at 0.5, 1, 1.5, 2, 4, 6, 8 and 12 hours (±30 min) post first dose on Day 1, at pre-dose and 2 hours (±30 min) post first dose on Days 2-7, 24 and 48 hours (±30 min) post Day 7 dose, and at Follow-up. 12-lead ECG will be done in triplicate at Screening, Check-in, Day 1 at pre-dose and 1, 2, 3, 4, 5, 6, and 8 hours (±30 min) post first dose, prior to first dose on Days 2-7, and on Day 8 (24 hours (±30 min) post-dose Day 7). Clinical labs will be assessed at Screening, Check-in, prior to first dose on Day 4, Day 8, and at Follow-up. HbA1c will be measured in serum at Screening. Prolactin will be measured in serum at Screening, Day 4, Day 9, and Day 15. C-SSRS will be assessed at Screening, Day 4, and Day 8. Subjects will remain in the clinic from Check-in to Discharge on Day 9 for additional safety assessment and then return for a Follow-up Visit on Day 15. Subsequent groups will follow the same study procedures.

When there are two or more procedure (ECG, Vital Signs, and PK) scheduled for the same timepoint, the procedures will be as close to the time point as possible and in the following order: ECG, Vital Signs, and then PK blood collection.

The PK profile will include AUC_{0-t}, AUC₀₋₂₄, AUC_{0-inf}, AUC_{wextrap}, CL/F, C_{max}, T_{max}, λ_z, and t_{1/2}.PK samples will be analyzed for all subjects in each cohort prior to dose escalation. These data will be used as adjunct information for a safety review, which will include a review of adverse events, changes in vital signs, physical examination and clinical laboratory test results.

If the starting dose (50 mg/day) for Cohort 1 (Part A) results in a total benzamide (LB-101 and LB-102) geometric mean C_{max} greater than 175 ng/mL or a geometric mean of total benzamide exposure (AUC_{inf}) greater than 3,270 ng/mL*h, the dose for Cohort 2 will be adjusted downward, to the nearest 10 mg, by the equations below (equations are based on the observed PK and assume dose linearity). The equation producing the lower dose will be selected. If the terminal phase PK is not captured adequately by the last time point collection, time will be extended to capture at least 2 time points of the terminal phase. Upon collection of the PK from Cohort 2, the human PK model will incorporate the human PK data and any elements of non-dose-linear PK. Dosing of the 3rd cohort will resume at 100 mg unless there is a clinical concern with safety in Cohort 2. If there is a clinical concern in Cohort 2, the SRC will convene and determine an appropriate dose for Cohort 3. Dose escalation is designed to at least capture the exposure range listed in Table 3 with the intent to exceed a C_{max} of 1,200 ng/mL and or an AUC_{inf} of 16,000 ng/mL*h (Refer to Section 6.8) unless there are clinical findings limiting further escalation. Dose escalation to 200 mg in Cohort 4 and 400 mg in Cohort 5 will be dependent on clinical observations.

 $Dose \ 2 = 50 \ mg * C_{max} \ 35 \ ng/mL \ / \ Observed \ C_{max} \ (ng/mL)$ or $Oose \ 2 = 50 \ mg * AUC_{inf} \ 655 \ ng/mL*h \ / \ Observed \ AUC_{inf} \ (ng/mL*h)$

Table 3: Target C_{max} and AUC_{inf} for Total Benzaminde Plasma Concentration Resulting from Dosing LB-102

Dose (mg)	C _{max} (ng/ml)	AUC _{inf} (ng/ml*h)
10	35	330
50	173	1648
100	346	3297
200	692	6593
400	1384	13186

A Safety Review Committee (SRC) will be assembled to review the blinded available study results for a cohort and agree whether the safety profile is sufficiently acceptable to support proceeding with the evaluation of the next higher dose level. The SRC will be comprised of the Investigator, Medical Monitor, and a Sponsor Representative (voting members). Other non-voting consultants, including to but not limited to, PK or medical expert, statistician, etc. may support the SRC on an as needed basis. Blinded data to be reviewed after each cohort includes, but is not limited to adverse events, physical examinations, vital signs, 12-lead ECGs, clinical laboratory safety tests, and concomitant medications/procedures. Blinded PK analysis will occur at the end of each Cohort (Cohorts 1-5) for the SAD study and after the 1st cohort for the MAD study.

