6.8 Selection of Dose in the Study

Comprehensive, Good Laboratory Practice (GLP)-compliant, 28-day, oral repeat-dose toxicity studies have been conducted on LB-102 in rats and dogs. For both species, LB-102 was administered using the intended clinical treatment regimen which included oral dosing twice per day approximately 12 hours apart. In rats, doses of 0, 20, 40 and 100 mg/kg/dose (0, 40, 80, and 200 mg/kg/day) and in dogs doses of 0, 0.75, 3 and 7.5 mg/kg/dose (0, 1.5, 6 and 15 mg/kg/day) were administered. For both species, a 1-month post-dose recovery period occurred following 28 days of treatment. LB-102-related effects in rats were associated with elevated levels of prolactin, which are presumed to occur with LB-102 based on its mechanism of action as a dopamine antagonist. These changes are unique to rodents, have been observed with other dopamine antagonists, were noted at all doses, and included hypertrophied corpora lutea (CLs), decreased CLs, interstitial cell hyperplasia and increased number of atretic follicles in the ovaries, mammary gland lobuloalveolar hyperplasia, and vaginal mucification in females and mammary gland atrophy and prostatic inflammation in males. Tissue changes either completely resolved or showed a trend to resolution during the recovery period. Given the species-specific nature of the response, the no-observed-adverse-effect-level (NOAEL) was determined to be 200 mg/kg/day, the highest dose administered. In dogs, the main finding was an increase in heart rate at 6 and

15 mg/kg/day. The dogs remained in sinus rhythm and, due to the lack of correlating clinical/veterinary observations, clinical pathology findings, or histopathological findings, this change was not considered to be adverse. Furthermore, no cardiovascular alterations were noted after the recovery period. The NOAEL was determined to be 15 mg/kg/day, the highest dose administered.

To determine, the initial starting dose in humans, the NOAEL doses in both species are converted to human equivalent doses (HED) using FDA's (2005) guideline entitled "Estimating the Maximum Safe Starting Dose in Initial Clinical Trials for Therapeutics in Adult Healthy Volunteers." These corresponded to 32 and 8.1 mg/kg/day in rats and dogs, respectively. Dogs are the most sensitive species, therefore, applying a safety factor of 10, the initial starting dose in humans is 0.8 mg/kg/day (approximately equivalent to 50 mg/day for a 60 kg adult).

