8.5.2 Dose Escalation

8.5.2.1 Part A

The study will begin at the lowest planned dose level (50 mg/day). Data from at least 6 evaluable subjects through 48 hours within the cohort are required for safety review by the SRC before dose escalation in the subsequent cohort, provided any discontinuations are not suspected of being related to LB-102. For purposes of dose escalation, an evaluable subject is defined as a subject who received a dose of LB-102 or placebo and has completed through 48-hour study procedures.

If the starting dose (50 mg/day) for Cohort 1 (Part A) results in a total benzamide (LB-101 and LB-102) geometric mean C_{max} greater than 175 ng/mL or a geometric mean of total benzamide exposure (AUC_{inf}) greater than 3,270 ng/mL*h, the dose for Cohort 2 will be adjusted downward, to the nearest 10 mg, by the equations below (equations are based on the observed PK and assume dose linearity). The equation producing the lower dose will be selected. If the terminal phase PK is not captured adequately by the last time point collection, time will be extended to capture at least 2 time points of the terminal phase. Upon collection of the PK from Cohort 2, the human PK model will incorporate the human PK data and any elements of non-dose-linear PK. Dosing of the 3rd cohort will resume at 100 mg unless there is a clinical concern with safety in Cohort 2. If there is a clinical concern in Cohort 2, the SRC will convene and determine an appropriate dose for Cohort 3. Dose escalation is designed to at least capture the exposure range listed in Table 3 with the intent to exceed a C_{max} of 1,200 ng/mL and or an AUC_{inf} of 16,000 ng/mL*h (Refer to Section 6.8) unless there are clinical findings limiting further escalation. Dose escalation to 200 mg in Cohort 4 and 400 mg in Cohort 5 will be dependent on clinical observations.

Dose 2 = 50 mg *
$$C_{max}$$
 35 ng/mL / Observed C_{max} (ng/mL) or
Dose 2 = 50 mg * AUC_{inf} 655 ng/mL*h / Observed AUC_{inf} (ng/mL*h)

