14. APPENDICES

14.1 Appendix 1: Clinical Pharmacology Summary Table

Table 1: Clinical Pharmacology Summary Table

Table 1: Clinical Pharmacology Summary Table General Information						
	I	Gei	neral Infor	mation		
	OSS HN HN	Weight: 383	N * H 3.51			
	Description	White to off-	white powder			
Chemical	рКа	9.36	9.36			
Structure and Major Physical	Partition Coefficient (LogP)	1.72 (pH 7)	1.72 (pH 7)			
and Chemical Properties	Aqueous Solubility	Vehicle	HPLC Area of Sample (225 nm)	Sample Concentration (mg/mL)	Calculated Solution Concentration (mg/mL)	Comment
		30% DMF 70% pH 4.7 MES	2769	0.44	44.0	100:1 dilution, pH of buffer is unchanged
		pH 4.7 MES Buffer	3770	0.614	61.4	100:1 dilution, pH of buffer is unchanged
		pH 5 HCl	4990	0.839	83.9	100:1 dilution, pH of buffer is unchanged
		pH 6 phosphate buffer	3827	0.625	625	1000:1 dilution, pH of buffer is unchanged
		pH 5 acetate buffer	Not Determined	>800	>800	pH of solution becomes 6.5
Indication (for this IND)	For the Trea	For the Treatment of Schizophrenia.				
Route and	Oral Capsul	Oral Capsule.				
Formulation Type (for this IND)						
Planned Strengths		LB-102 consists of API in a Size 2 white opaque/white opaque hard gelatin				
(for this IND)				ng, 50 mg, 75 n		
Planned Dose	For Part A (Single Ascending Dose Study) there were 5 dose levels: 50, 10, 100,					
Levels (for this	200, and 150 mg QD. For Part P. (Multiple Ascending Doses Study) there will be 3 dose levels (PID)					
IND)	For Part B (Multiple Ascending Doses Study) there will be 3 dose levels (BID), starting with 50 mg (100 mg/day). The remaining doses will be determined by the					

	SRC depending on the safety profile and clinical observations of the previous Cohort.
Mechanism of	The proposed mechanism of action for LB-102 is through dopamine D2/D3
Action (for this	receptor antagonism.
Indication)	

		Dose and AEs	
Therapeutic Dose and	Part A		
Exposure (for this IND)	Cohort	Treatment	
	1 (n=8) ^a	LB-102 50 mg (n=6) or Matching Placebo (n=2) QD x 1 day	
	2 (n=8) ^b	LB-102 10 mg (n=6) or Matching Placebo (n=2) QD x 1 day	
	3 (n=8) ^b	LB-102 100 mg (n=6) or Matching Placebo (n=2) QD x 1 day	
	4 (n=8) ^b	LB-102 200 mg (n=6) or Matching Placebo (n=2) QD x 1 day	
	5 (n=8) ^b	LB-102 150 mg (n=6) or Matching Placebo (n=2) QD x 1 day	
		Part B	
	6 (n=8)	LB-102 (n=6) 50 mg BID (100 mg/day) x 6 days (Days 1-6) and QD x 1 day (Day 7) or Matching Placebo (n=2) BID x 6 days (Days 1-6) and QD x 1 day (Day 7)	

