	7 (n=8)	LB-102 (n=6) Y* mg BID x 6 days (Days 1-6) and QD x 1 day (Day 7) Or Matching Placebo (n=2) BID x 6 days (Days 1-6) and QD x 1 day (Day 7)	
	8 (n=8)	LB-102 (n=6) Y* mg BID x 6 days (Days 1-6) and QD x 1 day (Day 7) Or Matching Placebo (n=2) BID x 6 days (Days 1-6) and QD x 1 day (Day 7)	
	at least 24 b – For Co Section 5. Y* - Dos observation	ort 1 (Part A), dosing of the first 2 subjects (1 active and 1 placebo) will commence hours prior to the remaining 6 subjects. Shorts 2-5, the doses may be reduced based on the PK results of Cohort 1 (Refer to 1). We will be determined by the SRC depending on the safety profile and clinical ons of the previous Cohort. We daily; BID = Twice daily	
	Treatment Exposure:		
	Part A: 1		
Maximum Tolerated	Part B: 7 Rats	days	
Dose	• I	n the 14-day repeat dose phase study, the maximum tolerated dose was determined to be 200 mg/kg/day	
	Dogs		
		n the single-dose phase of the dog range-finding study, the	
		naximum tolerated dose was determined to be 25 mg/kg/day	
		n the 14-day repeat-dose phase study, the maximum tolerated dose vas determined to be 5 mg/kg/day	

Principal Adverse Events	Prolactin elevation (≥ 100 ng/mL)			
	PK Features			
Dose/Exposure Range Tested in Clinic (Data	Single Dose	50 mg, 10 mg, 100 mg, 200 mg, 150 mg		
from this IND and/or Elsewhere)	Multiple Dose	N/A		
Range of Linear PK	At least to 200 mg (highest dose examined to date)			
Accumulation at Steady State	Repeat dose PK model suggests 40% of Cmax with b.i.d. dosing			
Metabolites	LB-101 approximately 2.5%			
Absorption	Absolute/Relative Bioavailability	N/A		
	Mean Tmax	50 mg - 3.000 h 10 mg - 3.000 h 100 mg - 2.833 h 200 mg - 2.083 h 150 mg - 3.167 h		
Distribution	Vd/F or Vd	N/A		
	% bound in plasma	N/A		
	Blood / plasma partition ratio	N/A		
Elimination	Route	Oral (PO)		
	Mean Terminal t½	50 mg - 12.311 h 10 mg - 13.675 h 100 mg - 14.656 h 200 mg - 12.835 h 150 mg - 12.620 h		
	Mean CL/F or CL	50 mg - 31.624 L/h 10 mg - 42.323 L/h 100 mg - 36.346 L/h 200 mg - 28.901 L/h 150 mg - 32.964 L/h		
Metabolism	• by CYP450 □ Yes □ No ⊠ NA, if yes, specify			
	• by Phase 2 enzymes □ Yes □ No ☒ NA			
	• by other enzyme systems \square Yes \square No \boxtimes NA, if yes,			

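### The protocol contradicts itself on figures that justify and bound the doses: the Cohort 5 dose, the AUC constants, the exposure range covered and the dog toxicology. These passages should be reconciled, the dog figures before Part B doses are selected.

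*Protocol*

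**What the plan says.** **Cohort 5.** The escalation paragraph of Section 5.1 and Section 8.5.2.1 both state "Dose escalation to 200 mg in Cohort 4 and 400 mg in Cohort 5 will be dependent on clinical observations". Another paragraph of Section 5.1 says that, after 50 mg, "subsequent groups will administered 10, 100, 200, and 150 mg/day, respectively". The tables in the Synopsis, Section 6.3 and Appendix 1 also give 150 mg. Appendix 1 uses the past tense for Part A ("there were 5 dose levels: 50, 10, 100", continuing with 200 and 150 mg) and reports PK and adverse events at all five doses.

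**Cohort 2 adjustment rule.** The rule applies if Cohort 1 (50 mg) gives a "geometric mean C_{max} greater than 175 ng/mL or a geometric mean of total benzamide" AUCinf above 3,270 ng·h/mL. Cohort 2 is then rescaled by two equations, one with a Cmax constant of 35 ng/mL and one with "AUC_{inf} 655 ng/mL*h / Observed AUC_{inf} (ng/mL*h"), and the lower result is taken. Table 3, in the same section, gives the target exposures by dose.

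**Exposure range.** Escalation is said to cover at least the Table 3 range, which ends at 400 mg, "with the intent to exceed a C_{max} of 1,200 ng/mL and or an AUC_{inf} of 16,000 ng/mL*h", subject to limiting clinical findings and with a reference to Section 6.8.

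**Dog data.** Section 6.8 reports a 28-day GLP study with twice-daily dosing: "The NOAEL was determined to be 15 mg/kg/day, the highest dose administered". Appendix 1 says that the dog MTD in a 14-day repeat-dose phase was "determined to be 5 mg/kg/day", and gives 25 mg/kg/day for a single dose.

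**The concern.** All of these statements are in current text. None depends on the summary of changes. They include a cohort dose, a decision threshold, a stated property of the design and the toxicology behind the starting dose, and as written they cannot all stand or are left unexplained. The SRC, the IRB or a later reader could take from the design text that Part A explored exposures up to the 400 mg row of Table 3, when it did not. Appendix 1 lists multiple dosing as not yet tested, and the doses of Cohorts 7 and 8 are still open, so there is time to correct the record before it is used.

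**Working it through.** **The plan's own figure.** Section 6.8: dog HED 8.1 mg/kg/day ÷ safety factor 10 = 0.81 mg/kg/day; × 60 kg = 48.6 mg, or about 50 mg. The starting dose reproduces from the NOAEL.

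**Item 1, Cohort 5.** 400 mg (Section 5.1 escalation paragraph, Section 8.5.2.1) against 150 mg (Section 5.1 design paragraph, Synopsis, Section 6.3, Appendix 1). This is a direct contradiction.

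**Item 2, adjustment rule against Table 3.**

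| Figure in the rule | Table 3 value | Ratio |
|---|---|---|
| Cmax trigger at 50 mg: 175 | 173 | 1.01 |
| Cmax constant: 35 | 35 (10 mg) | 1.00 |
| AUC trigger at 50 mg: 3,270 | 1,648 | 1.98 |
| AUC constant: 655 | 330 (10 mg) | 1.98 |

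The AUC trigger is 3,270/3,297 = 0.99 of the 100 mg row, so the two halves of the rule use different exposure scales.

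Operational effect:
- At its own trigger each equation returns 10 mg: 50 × 35/175 = 10.0 and 50 × 655/3,270 = 10.0.
- The lower result is taken, so the AUC equation governs only if 655/AUC < 35/Cmax, that is AUC/Cmax > 655/35 = 18.7 h. Table 3 at 50 mg has 1,648/173 = 9.5 h.
- At the Table 3 exposures for 50 mg (173 and 1,648) neither trigger is met.

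**Item 3, exposure reached.** The highest Part A dose is 200 mg. Table 3 gives:
- Cmax 692/1,200 = 58% of the aim.
- AUC 6,593/16,000 = 41% of the aim.
- In the 400 mg row, Cmax 1,384 exceeds 1,200, but AUC 13,186 is 82% of 16,000.

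Section 6.8 holds the toxicology and the starting-dose derivation. Neither 1,200 nor 16,000 appears there.

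Cross-check of Table 3 with the mean CL/F in Appendix 1 (AUC ≈ dose/CL/F):
- 50 mg/31.624 L/h = 1,581 ng·h/mL, 0.96 of Table 3.
- 200 mg/28.901 L/h = 6,920, 1.05 of Table 3 and 43% of 16,000.
- 10, 100 and 150 mg give 236, 2,751 and 4,550, which are 0.72, 0.83 and 0.92 of Table 3 (150 mg interpolated as 1.5 × 3,297).

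This is approximate. It uses a mean CL/F, assumed to be for LB-102 alone, whereas Table 3 is total benzamide; Appendix 1 puts the metabolite at about 2.5%.

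**Item 4, dog data.** NOAEL/MTD = 15/5 = 3.0. In the 28-day study both 6 and 15 mg/kg/day lie above the 14-day MTD, and Section 6.8 reports raised heart rate, judged not adverse, at those two doses. The rat figures agree (NOAEL 200, MTD 200 mg/kg/day), so the discrepancy is confined to the species that Section 6.8 calls the more sensitive.

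**The case against.** The strongest reply is that little of this can still affect a subject. Appendix 1 shows all five Part A cohorts dosed, so the 400 mg sentence and the Cohort 2 rule no longer direct anything. A trigger need not equal a target, the AUC pair is consistent with itself, and the Cmax equation would normally decide. This stands, and it reduces items 1 and 2 to errors in the record.

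On item 3, the aim is an intent, is worded as and/or, and yields to clinical findings. Appendix 1 reports a Grade 1 QTcF event and a Grade 2 acute dystonic reaction at 200 mg, and says openly that 200 mg is the highest dose examined. That may well explain the stop, but no passage says so, and the design text still describes a range up to 400 mg.

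On item 4, the NOAEL and MTD come from different studies. The regimen and dose-limiting finding of the 14-day phase are not given, so both figures may be right. This also stands. What remains is that a longer study reports no adverse effect at three times the dose called maximally tolerated in a shorter one, and the protocol is silent on it.

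Stronger readings are tempting, and the documents do not support them:
- *The SRC sets Part B doses against these figures.* Section 6.3 ties Cohorts 7 and 8 to the safety profile and clinical observations of the previous cohort. Sections 5.1 and 8.5.2.2 base Part B on PK observed in Part A. None refers to Table 3, the 1,200/16,000 aims or an animal margin.
- *These are the only exposure benchmarks.* Appendix 1 also holds observed human PK.
- *The animal margin for Part B is a third of what is claimed.* No Part B margin is stated, and scaling from the MTD would assume that it is the governing figure.

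**Conclusion.** The point holds as a set of passages to reconcile. The sizes are 400 against 150 mg for Cohort 5; AUC constants at 1.98 times Table 3 while the Cmax constants match; a highest dose predicted to reach 58% (Cmax) and 41% (AUC) of the stated aims, with a reference that leads nowhere; and a dog NOAEL three times the dog MTD. The percentages rest on Table 3 and dose-linearity.

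A reader might infer that Table 3 or the starting dose is unsound. That does not follow: Table 3 is linear in dose and lies within −28% to +5% of the AUC implied by observed CL/F, and the starting dose reproduces from its stated inputs. The first three items should be fixed as a matter of accuracy. The dog item should be settled before Part B doses are selected, because it bears on dosing still to come.

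**What to change.** Check the four items against the source toxicology and PK-model reports, then:

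1. Make the Cohort 5 dose in Sections 5.1 and 8.5.2.1 agree with the tables and Appendix 1.
2. Correct 3,270 and 655, or explain why the AUC figures sit at twice Table 3 when the Cmax figures do not.
3. State the exposure range that Part A covered and why escalation stopped at 200 mg. Give the source of the 1,200 and 16,000 aims, or remove the reference to Section 6.8.
4. Explain how the 28-day dog NOAEL and the 14-day dog MTD fit together (regimen, dose-limiting findings), before the SRC selects Part B doses.

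No dose is proposed here; which figures are right is for the sponsor to establish. The cost is wording and a check of source reports. The stated exposure range, or the factor resting on the dog data, may turn out less favourable.
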